Feasibility of a Soccer-based Adaptation of the Diabetes Prevention Program

Soccer DPP

Scientific Protocol

Principal Investigator - [name], Emory University Rollins School of Public Health, Global Health

Sponsor: Georgia Center for Diabetes Translation Research

NCT Number: NCT03595384

Protocol Version 3, dated 11-6-2018

Background and Rationale

Football (soccer) has proven successful as a health intervention globally, owing in large part to its extreme popularity with over 500 million active participants worldwide.(1) The Federation Internationale de Football Association (FIFA) developed the initiative “Football for Health” to help reduce NCDs starting in Africa (2) and later in adolescents in Mexico as “FIFA 11 for Health.”(1, 3) Additionally in 2010, FIFA marketed the evidence-based phrase “Playing football for 45 minutes twice a week – best prevention of NCDs.”(4) Soccer has also been leveraged to deliver lifestyle intervention programming in several European countries. (5, 6)

Recreational soccer (RS) is effective in reducing cardio-metabolic risk in both children and adults of all shapes and backgrounds, which stems from its varied movement patterns and highly functional training throughout a single session. (7) Generally, **RS participants achieve more than 100 high-intensity runs** and specific intense actions such as dribbles, shots, tackles, turns and jumps over a typical 1-hour training session, with **average heart rates being around 80% of maximal heart rate, irrespective of age, fitness status and previous experience of football training.** These high intensity intervals result in broad-ranging physiological effects such as reduced insulin resistance, chronic inflammation and arterial stiffness and have positive effects on T2DM and cardiovascular disease (CVD) risk factors.(8, 9) Evidence indicates that high intensity interval training (HIIT) modalities such as RS are not only highly efficacious but also safe and engaging interventions for cardio-metabolic risk reduction.(10-12) In addition, RS also builds social capital and is associated with positive motivational factors.(4)

In a two-arm, pragmatic, randomized controlled trial (n=747 men aged 35–65 years with a BMI of $\geq 28 \text{ kg/m}^2$) soccer program, an **average 4.36% weight-loss effect** (95% CI 3.64% to 5.08%) was reported in favor of the intervention.(13) Highly significant improvements on waist, percentage body fat, systolic and diastolic blood pressure, self-reported PA, diet and indicators of well-being and physical aspects of quality of life were also observed. At an estimated cost £862 per additional participant maintaining a 5% weight reduction at 12 months and £13,847 per additional QALY, compared with no active intervention, there was an **89% probability for the program to be cost-effective** at the prevailing £30,000/QALY threshold in the UK health care system.(13)

Adherence to PA in sedentary individuals is an ongoing challenge with barriers including lack of intrinsic motivation, time and resources.(14) Rate of perceived exertion plays a key role for PA sustainability in untrained individuals (15) and is lower when activity intensity is self-selected. (16) There is no difference between RS sessions of 3v3, 5v5 or 7v7 when the pitch is adapted for number of players. (17). **Despite the high heart rates, small-sided RS had the lowest perceived exertion rate** (4 out of 10) when compared to other forms of HIIT such as interval running. (17) This may **explain the high adherence rates (> 90%) for participants in RS interventions** and high enjoyment reports while also maintaining interest in playing RS even after the intervention period was over.(18) RS could be a key intervention to engage the Hispanic male community in Atlanta in health promoting PA.

Men, in general, are harder to engage in traditional disease prevention programs using traditional diet and PA interventions (19). Several studies have translated the DPP to be culturally-specific to the Hispanic community in various settings but predominantly in females.(20, 21) **Hispanic men are significantly understudied** and we are not aware of DPP translational programs tailored to Hispanic male populations. These community-based approaches had retention rates ranging between 63-93% after the core sessions at 6 months. These approaches worked well in females, but there was **little discussion on what drove the lack of recruitment in males.** Furthermore, previous DPP translation trials typically lack reporting of PA results, one of the pillars of the program, specifically objectively-measured PA.(22)

Using technology in an intervention setting can be a simple, efficient, motivational substitute to the traditional DPP format. An abbreviated mobile application version of the DPP was employed effectively in a multiethnic population in San Francisco. This study provided an iOS mobile app in combination with an in-person five month DPP. (23) This group of mostly middle-aged (mean 55 years) females had a retention rate of 93% at five months with a mean 7% weight loss. (23) A 13-week diabetes prevention program was implemented in Northern Mexico, in which 63% of the 184 participants completed the intervention. This mostly female cohort improved their fasting glucose by 7.5 ng/dL after a 3-month follow up. (24) In summary, the DPP can be adapted to a Hispanic community and abbreviated to coincide with a RS intervention.

Our objective is to harness the popularity of RS in local Atlanta Hispanic males and determine the feasibility of a RS implementation in combination with online education and facilitated lifestyle coaching to decrease T2DM

risk. Translating the DPP with a simple online tool and alongside a free opportunity to play a venerated sport in a supportive atmosphere may prove to be exactly what is needed for adherence in Hispanic males.

Protocol Synopsis

Study Design: A longitudinal pre-post pilot intervention study evaluating feasibility of implementation of a soccer-based Diabetes Prevention Program and preliminary changes in physical activity and diet-related measures.

Planned Sample Size: 40 subjects

Subject population: Hispanic overweight males age 35 to 55 years with a CDC pre-diabetes risk score ≥ 9 and not currently engaged in soccer or other regular physical activity.

Specific Aims

We will test the following central hypothesis: **A soccer-based adaptation to the DPP can be feasibly implemented in a population of middle-age Latino men at high risk for T2DM.**

Aim 1: *1a:* To adapt the current National Diabetes Prevention Program (NDPP) curriculum to a novel, translational soccer-based DPP programming and delivered by trained coaches as facilitators.

1b: To conduct formative research addressing barriers and acceptability for implementation of this soccer-based DPP adaptation among Latino adults via questionnaires and key informant interviews.

Aim 2: *2a:* To assess implementation feasibility of this novel soccer-based DPP adaptation by conducting a single-arm, pre-post pilot study among Latino males (n=40; 35-55 years) residing in the Atlanta metro area.

2b: To explore preliminary signals for improvements in objectively-measured PA, dietary behaviors, physical fitness and body composition outcomes with our soccer-based DPP adaptation.

Overweight (BMI between 25 and 60 kg/m²) participants at high risk for T2DM (CDC pre-diabetes screening tool score >9)(25) will be recruited through soccer interest groups, local leagues and Hispanic health organizations. After a baseline assessment visit, participants will attend soccer practice twice/week for 12-weeks while completing NDPP core curriculum modules with facilitated discussion by trained coaches during each soccer practice. Participants will then be invited to join an established small-sided soccer league in their community (12-weeks) offering one game/week and also complete the NDPP maintenance modules and PA/diet self-tracking via mobile health technologies. After the core (12-weeks) and maintenance intervention periods (24- weeks) baseline measurements will be repeated. We will also conduct a 1-year follow up assessment after 6 months of minimal contact. Data on the feasibility of this DPP soccer-based adaptation will inform future randomized, controlled trials testing the effectiveness of this translation model to reduce T2DM risk while extrapolating to other sports-based adaptation and age, gender and racial sub-populations.

Research Design:

Organizational structure of study team: This study was investigator initiated and proposed to the Georgia Center for Diabetes Translation Research at Emory University as part of an internal pilot grant. The funder's expectation was for the investigator to conduct feasibility or pilot research to support a larger grant. Funder will provide a speedtype for all expenses related to the study.

Setting: Aim 1 will be conducted in the field at Latino community health fairs put on by Ventanillas de Salud. The majority of Aim 2 will be conducted on rented soccer fields, no permission is needed to conduct the study, but field owners are aware of the study be conducted. All data will be collected on paper and transferred to a RedCap database at Emory University Rollins School of Public Health.

Aim 1a. During the first phase of this pilot study, we will adapt the CDC's NDPP to an electronic online curriculum dissemination, accelerated to conform to our planned 24-week soccer intervention while maintaining the separation between core and maintenance modules.

Experienced soccer coaches will be identified and hired from the local area to deliver the RS program. These coaches will be trained in two key aspects of the program: 1) leading small-sided RS training designed to safely

engage pre-diabetic participants in HIIT conditioning; 2) facilitate the lifestyle coaching in the NDPP curriculum by devoting time during each soccer training session to reviewing the NDPP material, fostering discussion and using the groups' social dynamics to promote sustained lifestyle behavior change and increase self-efficacy. These coaches will be the primary facilitator of the study, conducting both soccer specific activities and online education discussion. The study staff will conduct consent and all measurements and assessments.

Aim 1b. Secondly, we will conduct a brief survey among middle-aged adult Latino community members to determine potential barriers to participation in the soccer-adapted NDPP program and usability of mobile health technologies. These interviews will inform scheduling and recruitment for Aim 2. We will focus recruitment in Clayton (13%), Cobb (12.8%), and Gwinnett (20.5%) counties which have the highest percentages of Hispanic residents.

Aim 2. We will conduct a pilot feasibility study in 40 males recruited from the local Atlanta community.

Inclusion criteria

- 1) Hispanic/Latino men aged 35-55 years
- 2) BMI $\geq 25 \text{ kg/m}^2$
- 3) CDC pre-diabetes risk score ≥ 9 (25)
- 4) Not currently engaged in soccer practice or league or other PA or lifestyle intervention program
- 5) Ability to read in English or Spanish and provide informed consent

Exclusion criteria

- 1) T2DM diagnosis or medication
- 2) BMI ≥ 41
- 3) Resting blood pressure $\geq 165/100$ at screening
- 4) Any mobility issues or contraindications for HIIT PA program (26)

Recruitment: Participants will be recruited from the mentioned local Atlanta area organizations using online a study recruitment flier in both print and electronic format. Interested participants will be provided an online survey to ascertain eligibility (CDC pre-diabetes screening, demographic questions and PA habits) and those meeting inclusion criteria will be invited to an informative session at one of participating soccer field for informed consent and confirmatory baseline assessments including BMI, blood pressure, HbA1c and exercise pre-participation risk screening. Siemens DCA Vantage HbA1c point-of-care devices will be used for screening of diabetes. (27) A cut off point of 6.5% will be used as a putative definition of diabetes and these individuals will be referred to a local clinic for confirmatory testing and appropriate management. (28) Both systolic and diastolic blood pressure will be measured while sitting using a calibrated electronic blood pressure sphygmomanometer prior to any activity and after five minutes of rest. Participants meeting inclusion and exclusion criteria will be invited to participate in the study.

Study Assessments. Prior to testing, subjects will be asked to refrain from physical activity for 48 hours prior to test day, refrain from alcohol 24 hour prior to testing, and refrain from caffeinated drinks, smoking and other stimulants one hour prior to testing. Assessments will be conducted at baseline during the first soccer practice and after the 12-week initial soccer conditioning phase. Assessments will also be repeated at 24-weeks and 1 year from study initiation at the final monthly meeting after the soccer league (maintenance phase of the program) has been completed. Blood pressure, HbA1c, height and weight, waist circumference, aerobic and musculoskeletal fitness assessments will be performed. In addition, questionnaires will be used for self-reported physical and mental health, quality of life, PA and diet self-efficacy, program satisfaction and injuries. Dietary recalls will be conducted at baseline, 12, 24 weeks, and 1 year and by trained staff and analyzed using Nutrition Database System for Research.(29) Participants will participate in online education modules located on the CDC website during an initial 12 week conditioning phase where they will participate in soccer drills and other fitness routines (two 1-hour sessions per week). At the 12 week mark participants will transition onto a soccer league team for the following 12 weeks where they will continue to complete online modules and meet with the soccer coach monthly to discuss. There will be a 1-year follow up to be conducted 6 months from the final soccer session to complete all measurements again. During the soccer sessions/games participants will

be fitted with a wearable soccer-specific device to measure how much they move and their heart rate. All of these measurements will be done on the soccer field. In addition, they will also be asked to wear a Garmin fitness tracker for the duration of the study to measure steps and moderate and vigorous activity. The online education will be a version of the Diabetes Prevention Program and can be completed on a phone or computer with internet access. We will send reminders by text message to do the online education and the soccer coach will talk to the soccer team during soccer practice about what they've learned and answer any questions they may have about the education material.

Informed Consent Process:

Adult consent forms in both English and Spanish will be prepared for this study. The consent form will describe the purpose of the study, the procedures and risks. Participant will be presented with the consent form by the PI of the project, who is a native Spanish speaker and has conducted many research studies in the Hispanic community in the US as well as Latin America, in person and given time to read and ask questions. A signed consent form will be obtained from the participant. A copy of the consent form will be given to the participant and this process will be documented.

Risks:

There is minimal risk in this study. Potential risks are related to 1) Finger sticks 2) Physical injury related to sport and 3) Confidentiality. 1) A single-use finger stick device will be used during assessments along with alcohol to clean the site prior to stick to reduce chances of infection. 2) Exercise can cause muscle soreness, weakness and in some cases muscle strains, ligament sprains and rarely bone fractures can occur. In very rare cases exercise can induce chest pain or a heart attack or other medical emergency. The training program led by the soccer coach is designed to minimize risk of injuries or events by slowly progressing on the practice of soccer using soccer and exercise drills appropriate for your age and level of fitness. Soccer sessions will be led by trained professionals who are able to offer suggestions to limit and prevent these adverse events. They are trained to recognize medical emergencies, will have basic equipment available, and seek emergency care if needed. 3) There is a risk of loss of confidentiality. Efforts will be made to keep all personal information confidential. All data will be stored in locked offices and password-protected computers. Personal identity will be protected in any publication.

Benefits: There are no direct benefits of this study beyond opportunity to exercise and information about healthy behaviors.

Compensation:

Participants will receive free entry into soccer leagues in their local area for the maintenance portion of the study. (A ~\$100 value) Subjects that complete the study will be allowed to keep the Garmin fitness tracker.

Data Analytics and Statistical Plan:

Data and statistics will be managed by the PI and the study team using RedCap. Any paper forms will be kept in a locked cabinet in a locked office. Demographics and characteristics of the overall cohort will be tabulated using means and standard deviations or counts and percentages, as appropriate. Prior to analysis, continuous measures will be tested for normality. Non-normally distributed variables will be transformed prior to analysis or non-parametric approaches will be utilized. Linear regression will be used to control for anthropometrics and other factors that may influence improvement and will contain no more than five predictors at a time, given our sample size of 40. Standardized mean differences and effect sizes with associated 95% CI will be calculated for outcomes of interest.

Training of study team:

As stated above all staff and soccer coaches will receive adequate training of all study procedures. All study staff and collaborators will take CITI training upon hire.

Confidentiality: Screens will be used on the soccer fields for consent and study measurements. All participants will receive a study ID and this will be used on all paper and electronic forms. We will destroy all identifiers and any audio from key interviews after the study is complete.

References

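### Do the loose timing of baseline HbA1c and the unstated effect of a 6.5% result on eligibility call for a change to the plan?

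*Combined protocol and SAP*

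**What the plan says.** The Recruitment section sets out a sequence. Men who pass an online survey come to a session at a soccer field for "informed consent and confirmatory baseline assessments including BMI, blood pressure, HbA1c and exercise pre-participation risk screening". The purpose of the HbA1c test is then given: "Siemens DCA Vantage HbA1c point-of-care devices will be used for screening of diabetes". The rule for reading it follows: "A cut off point of 6.5% will be used as a putative definition of diabetes". For men who reach it, "these individuals will be referred to a local clinic for confirmatory testing and appropriate management". The section ends: "Participants meeting inclusion and exclusion criteria will be invited to participate in the study".

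The first entry under Exclusion criteria is "1) T2DM diagnosis or medication". Human Subjects Involvement and Characteristics repeats it. Neither list gives an HbA1c value.

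Two other places describe the baseline. Specific Aims says: "After a baseline assessment visit, participants will attend soccer practice twice/week for 12-weeks". Study Assessments says: "Assessments will be conducted at baseline during the first soccer practice and after the 12-week initial soccer conditioning phase". It has the assessments repeated at 24 weeks and 1 year, and it includes HbA1c among the measurements.

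On treatment begun after entry, the documents are silent. Medication does not appear among the questionnaires in Study Assessments or in the Research Material Collected list, which is not worded as exhaustive. The section on potential benefits foresees new diabetes diagnoses during the study and provides for telling and referring the man.

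**The concern.** Three sections use the word baseline for events that do not obviously coincide: a session before invitation, a visit before practice starts, and the first practice itself. If there is one HbA1c reading, the sections disagree on whether it precedes invitation. If there are two, nothing says which one starts the before-and-after comparison.

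The eligibility rule also looks incomplete. A provisional result that still needs confirming is not yet a diagnosis, and diagnosis or medication is what the exclusion list names. Two members of staff could class the same referred man differently, one as a screen failure and one as a participant.

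Finally, a man who starts glucose-lowering treatment during the year may show a fall in HbA1c, and possibly a change in weight, that has nothing to do with soccer. With no control group and no stated record of treatment, that fall could be read as a programme effect.

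**Working it through.** There is no sample size, power or error rate to recompute, so the check sets the sections side by side.

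1. **Where the cut-off applies.** The 6.5% figure occurs once, in Recruitment, directly after the statement that the device is used for screening and before the sentence on invitation. Study Assessments mentions no cut-off. If there are two readings, the 6.5% rule therefore belongs to the screening one.

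2. **Timing.** Recruitment deals with eligibility checks, and Study Assessments with the repeated outcome schedule. A screening reading followed by an outcome reading at the first practice fits both. The before-and-after series then starts at the first practice, the reading that Study Assessments sets in sequence with 12 weeks, 24 weeks and 1 year. The visit in Specific Aims precedes practice and so fits the Recruitment session. Its one mismatch is with Study Assessments, over whether baseline comes before the first practice or during it. Both can mean measurement before training has begun: Study Assessments asks men to avoid physical activity for 48 hours before a test day, and Recruitment has blood pressure taken before any activity.

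3. **If only one reading is taken.** The Recruitment value then serves both purposes and still precedes the intervention. Selecting men below an upper limit on that same value would tend to make later readings drift slightly upwards, which works against an apparent improvement.

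4. **Eligibility.** Taken in order, the text screens for diabetes, refers men at the cut-off, and then invites those who satisfy the criteria, the first exclusion being type 2 diabetes. Exclusion is the natural reading. What stays unwritten is the status of a man whose confirmation is pending.

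5. **Later medication.** Aim 2b names physical activity, diet, fitness and body composition, and describes them as preliminary signals. HbA1c is not among them. The first exclusion criterion implies that diabetes medication is asked about at entry, so the silence concerns later visits only. The study's own HbA1c at 12 weeks, 24 weeks and 1 year would show which men had since reached the referral level. The Data Analytics and Statistical Plan lets the regression include other factors that may affect improvement, within its limit of five predictors.

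6. **Counts.** Recruitment and Informed Consent gives 70 screened and 30 failures: 70 − 30 = 40 enrolled, 40/70 = 57.1% and 30/70 = 42.9%. The arithmetic is consistent. Each man moved from enrolled to failed would cost 1/70 = 1.4 percentage points of yield. The 30 are not split by reason, and no number of men at 6.5% or above is given. If such men are already among the 30, the effect is zero. The documents give no basis for any other figure.

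**The case for a change.** The strongest case for acting is that clarification is cheap and the ambiguity is real. All three sections say baseline, and none says there are two readings. The protocol itself treats the result as provisional, so inferring exclusion from the diagnosis criterion leaves a step unwritten. The blood pressure criterion, by contrast, states both its value and that it applies at screening. Since the programme is aimed at men at high risk of diabetes, whether men with probable diabetes are enrolled bears on who is studied. Referral for management also makes new treatment foreseeable during follow-up.

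Part of this stands. Specific Aims and Study Assessments do not match on the timing of baseline, the status of a man awaiting confirmation is not stated, and recording of new medication is not mentioned. None of it shows that following the plan would give a wrong result. Silence in a list that is not exhaustive does not show that medication goes unrecorded. The order of measurement does not decide eligibility either: a man tested at the first practice can still be found ineligible under the exclusion list. The possible effect of treatment on weight is conceivable, but the documents give no figure for it, and an uncontrolled before-and-after change could not be attributed to the programme even with perfect medication records.

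**Conclusion.** The concern identifies loose wording, not a flaw in the design or analysis. It is a gap that staff and analysts can fill sensibly: the 6.5% rule governs the screening reading, and the first-practice reading opens the outcome series. No effect on feasibility or on any outcome named in Aim 2b is shown, and the effect on enrolment cannot be quantified from the documents and may be zero.

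This rests on three assumptions: that the screen-then-invite order in Recruitment is followed, that baseline measurements precede training, and that HbA1c change, if reported, is presented as descriptive. The status of a man awaiting confirmation is for the investigators to settle, and no rule is proposed here. The timing statements in Specific Aims, Recruitment and Study Assessments, and the screening paragraph against the two exclusion lists, can be reconciled as an editorial matter without altering the plan.

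### The 24-week field assessments are scheduled at a coach meeting that closes an invitation-only league phase, with no stated route to measure men who have left, so pre-post changes may over-represent adherers; the 1-year timing also contradicts itself

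*Combined protocol and SAP*

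**What the plan says.** Study Assessments (under Research Design) gives the occasion for the later measurements: "Assessments will also be repeated at 24-weeks and 1 year from study initiation at the final monthly meeting after the soccer league". The assessments listed there are blood pressure, HbA1c, height and weight, waist, and aerobic and musculoskeletal fitness, followed by questionnaires that include satisfaction and injuries.

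The only monthly meetings described are in the same section, where men in the league phase "continue to complete online modules and meet with the soccer coach monthly to discuss".

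On joining the league, Specific Aims says: "Participants will then be invited to join an established small-sided soccer league in their community (12-weeks) offering one game/week". Study Assessments puts it less conditionally: "At the 12 week mark participants will transition onto a soccer league team for the following 12 weeks".

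On the 1-year visit there are two further statements. Study Assessments says: "There will be a 1-year follow up to be conducted 6 months from the final soccer session to complete all measurements again". Specific Aims says: "We will also conduct a 1-year follow up assessment after 6 months of minimal contact".

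The Aim 1a text gives all measurement to study staff, not coaches. The stated retention aids are text messages (Protection of Human Subjects) and, for completers, keeping the fitness tracker (Compensation). Data Analytics and Statistical Plan names no analysis set and no method for missing data.

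**The concern.** The stated occasion for the 24-week measurements is itself a programme event, at the end of a phase that a man may decline or leave. If the schedule is followed literally, adherence decides who is measured. No section gives a separate visit, contact attempts or any other way to reach men who have left.

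There is no control arm, so change from baseline is the whole of the Aim 2b result, and Specific Aims says the data will inform later randomised trials. If men who stop attending also change less, the mean among those measured is too favourable for the cohort that enrolled. The satisfaction and injury questionnaires probably share the problem: men who left because they were dissatisfied or hurt would be among those least likely to be asked.

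**Working it through.** **Sequence of dates.** The core phase is 12 weeks and the league phase another 12, so the programme ends at 12 + 12 = 24 weeks. A closing coach meeting fits the 24-week assessment. Six months (about 26 weeks) after the last session is about 24 + 26 = 50 weeks, which fits a 1-year visit. The meeting sentence attaches the 1-year assessment to an occasion about six months too early for that. The other two statements agree with each other and not with the meeting sentence.

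**Which outcomes are tied to the meeting.** Weight, waist, blood pressure, HbA1c and fitness are. The questionnaires probably are. Dietary recalls have no stated venue, and the tracker is to be worn throughout the study, so diet and tracker-measured activity are not expressly tied to it.

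**Illustration of size.** The plan gives no dropout rate for this trial and no figure for this bias, so there is nothing to reproduce. Inputs:

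- N = 40 (Protocol Synopsis).
- Retention of 63% to 93%, borrowed from Background and Rationale: "These community-based approaches had retention rates ranging between 63-93% after the core sessions at 6 months". Applying it here is an assumption.
- k, the mean change in unmeasured men divided by that in measured men. This is unknown, so 0, 0.5 and 1 are shown.

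Number measured: 0.63 × 40 = 25.2, about 25; 0.93 × 40 = 37.2, about 37.

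With r the share measured, the all-enrolled mean is the measured mean times r + k(1 − r). The overstatement factor is therefore 1 / (r + k(1 − r)).

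| Measured of 40 | r | k = 0 | k = 0.5 | k = 1 |
|---|---|---|---|---|
| 25 | 0.625 | 1/0.625 = 1.60 | 1/0.8125 = 1.23 | 1.00 |
| 37 | 0.925 | 1/0.925 = 1.08 | 1/0.9625 = 1.04 | 1.00 |

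**Precision.** The 95% half-width for a mean change, in SDs of the change, is t(0.975, n − 1)/√n: 0.41 with 25 men and 0.33 with 37, against 0.32 with all 40. Precision suffers modestly; the main issue is who is missing.

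I have not converted the factors into percentage points of weight. The 4.36% in Background and Rationale is a randomised between-group effect, not a pre-post change among attenders.

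**The case against.** The strongest reply is that the sentence gives a time and place, not an attendance condition. Specific Aims says without qualification that the baseline measurements are repeated after each phase, study staff do the measuring, and nothing bars them from seeing a man who has left. Study Assessments also has participants moving to a league team as a matter of course, with fees paid and retention aids in place. This stands to a degree. A reader might infer that leavers will certainly be missed and that the results will describe adherers only; the documents do not say so. They support only that leavers may be missed, because no route to them is stated. The wording about moving to a team states an intention and does not stop a man from ceasing to attend.

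A reader might also infer that the 1-year result is selected by venue in the same way. It is not shown to be: two statements place that visit on a different occasion, so what remains is a contradiction. Nor does the argument extend to every Aim 2b outcome. Diet and tracker data could still be lost from leavers, but not through this mechanism.

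The illustration is open to challenge too. The retention range comes from other, mostly female programmes, and nothing links their losses to where assessments were held. Background and Rationale also cites adherence above 90% in recreational soccer. At 36 of 40 measured the factor is 1/0.90 = 1.11 with no change in absent men, and 1/0.95 = 1.05 with half the change. So the 1.6 is an upper-end case, not an estimate.

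Baseline and 12-week values could support a missing-data model. That is true, but none is planned, and it would rest on untestable assumptions about men who left. Finally, this is a feasibility pilot with exploratory outcomes, and retention is itself a finding. That lowers the stakes without removing the gap.

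**Conclusion.** The point holds for the 24-week field measurements and probably for the questionnaires. The one stated occasion for them depends on continued participation, and no alternative is given, so the pre-post changes may over-represent adherers. The direction assumes that men who leave change less than men who stay. The size cannot be known from the documents. Under the borrowed retention range the factor runs from 1.6 down to 1.08 with no change in absent men, from 1.23 to 1.04 with half the change, and is 1.00 with equal change.

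The 1-year wording is a separate and certain inconsistency, but only of schedule and setting. Both matters should be corrected; neither undermines the feasibility aim.

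**What to change.** In Study Assessments, state that every enrolled man is invited to the 12-week, 24-week and 1-year assessments whether or not he joined the league or attends meetings. Offer non-attenders a separate slot with study staff, covering at minimum weight and the questionnaires. In the analysis section, commit to reporting the number measured at each time point beside each change. Take the 1-year visit out of the sentence about the last monthly meeting, so that it agrees with the other two statements of its timing.

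The cost is a wording change and some staff time to contact and schedule men who left. It needs no new procedure and no extra participants.
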